6.4 Overdose

Patients will be admitted to AMC hospital (known symptoms:

6.5 Pregnancy

Pregnancy test will be performed at inclusion, since all females will be postmenopausal no checkup will be done thereafter

6.5.1 Maternal exposure

Pregnancy test will be performed at inclusion, since all females will be postmenopausal no checkup will be done thereafter

6.5.2 Paternal exposure

Will not be studied

6.6 Management of toxicities <<Dose Reductions>>

Will not be studied

6.7 Study governance and oversight

6.7.1 Steering Committee

Will not be installed

6.7.2 Data Monitoring Committee

Study will be monitored by Clinical Research Unit of the AMC (head: [name])

6.7.3 Scientific Advisory Committee

Will not be installed

7. INVESTIGATIONAL PRODUCT AND OTHER TREATMENTS

7.1 Identity of investigational product(s)

Investigational product	Dosage form and strength	Manufacturer
Dapagliflozin	10mg 1dd	Astrazeneca

Rosuvastatin

10mg 1dd

Astrazeneca

<>>

7.2 Dose and treatment regimens

10mg dapagliflozin once daily for 5 weeks ; rosuvastatin 10mg once daily for 9 weeks. Both will be supplied by AstraZeneca Netherlands, free of charge.

7.3 Labelling

Will be done by AMC clinical pharmacy

7.4 Storage

Will be done at AMC clinical pharmacy

7.5 Compliance

Will be checked by physician and nurse countil returned pills

7.6 Accountability

Will be done by AMC clinical pharmacy

7.7 Concomitant and other treatments

Restricted Medication/Class of drug:	Usage:
insulin	

Prohibited Medication/Class of drug:	
insulin	

Rescue/Supportive Medication/Class of drug:	Usage:
n/a	

7.7.1 Other concomitant treatment

7.8 Post Study Access to Study Treatment

Both rosuvastatin and dapagliflozin can be prescribed by physicians in the Netherlands

8. STATISTICAL ANALYSES

8.1 Statistical considerations

8.2 Sample size estimate

Previous studies have reported a 10 % increase in fasting plasma LDL plasma levels upon dapagliflozin 10mg once daily treatment in DM2 patients on statin therapy (20) As it can be expected that metabolic effects of SGLT2 inhibition stabilize after 4 weeks (5,6) and lipid fluxes upon intervention are usually determined upon 4-5 weeks after start of intervention (21), we suggest to treat for 5 weeks. A reduction was seen in 8 DM2 subjects of plasma LDL (from 3.1 ± 0.8 to 1.5 ± 0.4 mmol/l) on rosuvastatin treatment, that corresponded with a similar decrease in LDL- ApoB poolsize /synthesis (2.8 ± 0.4 to 1.5 ± 0.4 gram/day, see ref 22) . We thus expect 10% higher plasma LDL level (from 3.1 ± 0.8 to 1.7 ± 0.4 mmol/l) with concomitant less decrease in LDL- ApoB poolsize /synthesis (1.8 ± 0.4 gram/day) upon rosuvastatin combined with dapagliflozin 10mg treatment in DM2. Using single sided test (with alfa of 0.05 and 85% power) and using difference in LDL-apoB synthesis of 0.3 gram/day with SD of 0.4, the sample size needs to be 11 DM2 subjects, on dapagliflozin 10mg treatment. Taking a 10% patient dropout rate, we aim to include 12 DM2 subjects in total.

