3.4 Procedures for handling incorrectly enrolled or randomized subjects

Patients will be replaced by new patients until all 12 DM2 patients have completed the trial

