8.4 Outcome measures for analyses

8.5 Methods for statistical analyses

8.5.1 Analysis of the primary variable(s)

All data will be analysed using SPSS for Windows, version 20.0 (SPSS Inc. Chicago, Illinois, USA). Multivariate analysis and ANOVA for repeated measures will be used. Wilcoxon's signed-rank test will be used to compare results between the study groups. Data will be expressed as median and range. Spearman's rank test will be used to calculate correlations.

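### Eleven subjects do not give the stated 85% power: on the plan's own inputs power is at most 80%, about 75% by paired t-test and about 70% by the exact Wilcoxon test

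*Combined protocol and SAP*

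**What the plan says.** The sample size paragraph appears in section 1.2 and again in section 8.2. It sets the error rates, "Using single sided test (with alfa of 0.05 and 85% power", and the effect, "using difference in LDL-apoB synthesis of 0.3 gram/day with SD of 0.4". It concludes that "the sample size needs to be 11 DM2 subjects" and then adds: "Taking a 10% patient dropout rate, we aim to include 12 DM2 subjects in total".

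The synopsis describes a single-arm trial, and section 8.3 defines the comparison as before against after dapagliflozin, so the calculation is for one group measured twice. For the primary variable, section 8.5.1 names multivariate analysis and repeated-measures ANOVA, and then says: "Wilcoxon's signed-rank test will be used to compare results between the study groups". It does not say which of these is the primary test.

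On dropouts, section 3.4 says: "Patients will be replaced by new patients until all 12 DM2 patients have completed the trial". Sections 3.9.1 and 3.10.2 repeat that rule.

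**The concern.** With a standardised effect of 0.3/0.4 = 0.75, 11 subjects looks too few for 85% power. The dropout step looks short as well, and it conflicts with the replacement rule. What is at stake is the error rate claimed for the primary outcome, change in LDL synthesis. A reader of sections 1.2 and 8.2 would believe that a true 0.3 g/day increase would be missed 15% of the time. If the real figure is 20% to 30%, a null result in this small uncontrolled study would be taken as stronger evidence of no effect than it is.

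**Working it through.** **Inputs (section 8.2).** One-sided alpha 0.05 (z = 1.645); power 85% (z = 1.036); difference 0.3 g/day; SD 0.4 g/day, read as the SD of the within-subject change; one group, before against after.

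**Reproducing the plan's 11.** Normal approximation for one sample of differences: n = ((z_alpha + z_power) × SD / difference)².

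- At 85% power: ((1.645 + 1.036)/0.75)² = 12.78, so 13.
- At 80% power: ((1.645 + 0.842)/0.75)² = 10.99, so 11.

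The plan's figure is therefore the 80% answer. Other variants move further from 11: at 85% power, a two-sided test needs 16 by the same formula, and two independent arms (one-sided) need 26 per arm.

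**Power at the planned sizes.** Three methods were used, all one-sided at 5%:

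- Normal: power = Φ(0.75√n − 1.645). For n = 11, 0.75 × 3.317 − 1.645 = 0.843, giving 80.0%.
- Paired t: noncentral t with n − 1 degrees of freedom and noncentrality 0.75√n.
- Wilcoxon signed-rank: 400,000 simulated samples of normally distributed changes, against the exact null distribution.

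| Completers | Normal | Paired t | Exact Wilcoxon |
|---|---|---|---|
| 11 | 80.0% | 74.8% | 69.9% |
| 12 | 83.0% | 78.5% | 75.5% |
| 13 | 85.5% | 81.7% | 79.3% |
| 15 | 89.6% | 86.8% | 84.7% |

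The smallest n for 85% is 13 (normal), 15 (paired t; 14 gives 84.4%) and 16 (exact Wilcoxon, 86.7%). The large-sample Wilcoxon without continuity correction gives 73.6% at n = 11 and 78.5% at n = 12. With two time points, repeated-measures ANOVA is equivalent to a two-sided paired t-test, whose power is 61.2% at n = 11 and 65.8% at n = 12.

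**Risk of missing the effect, against the implied 15%.**

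- Paired t at n = 12: 21.5/15 = 1.4 times.
- Exact Wilcoxon at n = 11: 30.1/15 = 2.0 times.
- Normal approximation: 17.0/15 = 1.1 times at n = 12 and 20.0/15 = 1.3 times at n = 11.

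**Difference detectable with 85% power (one-sided paired t).** 0.348 g/day at n = 11 and 0.331 g/day at n = 12.

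**Dropout.** 11/(1 − 0.10) = 12.2, which rounds up to 13. Twelve enrolled leaves 12 × 0.9 = 10.8 expected completers. If each subject independently has a 10% chance of dropping out and none is replaced, paired-t power averaged over the number of completers is about 74%. If dropouts are replaced until 12 complete, the n = 12 row applies and the 10% allowance does nothing.

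**The case against.** The strongest objection is that section 8.2 never calls 0.4 the SD of the change. It also gives 0.4 as the SD at a single time point in the cited rosuvastatin study, "2.8 ± 0.4 to 1.5 ± 0.4 gram/day, see ref 22". If 0.4 is cross-sectional, the SD of the change is 0.4 × √(2(1 − r)), where r is the before-after correlation, which the plan does not give. Over an assumed range of r, one-sided paired-t power at n = 11 is 50% (r = 0), 60% (0.25), 75% (0.5), 83% (0.6) and 91% (0.7). At n = 12, r = 0.6 gives 86%. True power could therefore exceed 80%.

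This makes the ceiling of 80% conditional on the SD reading, but it does not rescue the 85%. The sentence attaches the SD to the difference, and 11 is reproduced exactly (at 80% power) when 0.4 is the SD of the change, which is the same as r = 0.5. Reaching 85% by paired t needs r of about 0.63 at n = 11 or 0.59 at n = 12, and nothing in the plan supports such a value.

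Three smaller points stand in part. Under the replacement rule the relevant number is 12 completers, and by the normal approximation the shortfall is then only 2 points; but that approximation treats the SD as known, and none of the methods named in section 8.5.1 does. The 70% Wilcoxon figure assumes the exact test and normally distributed changes, and section 8.5.1 does not make Wilcoxon the sole primary test. The dropout shortfall is one patient of rounding, and it disappears if dropouts are replaced.

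The study is labelled a pilot, but it still states a formal power for its primary outcome, and that statement should be correct.

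**Conclusion.** The concern holds. With one-sided alpha 0.05, a difference of 0.3 g/day and 0.4 as the SD of the change, neither 11 nor 12 completers gives 85% power under any of the tests considered. The shortfall at n = 11 is 5 points (normal), 10 (paired t) or 15 (exact Wilcoxon); at n = 12 it is about 2, 6.5 or 9.5. The likeliest explanation is that 11 was calculated for 80% power. The figures rest on the reading of the SD, and the Wilcoxon figures also on normally distributed changes. The two rules for the number 12 contradict each other, and neither restores the stated power. Because this is the power claim for the primary outcome and is wrong as written, it must be corrected.

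**What to change.** 1. In sections 1.2 and 8.2, state that 0.4 g/day is the SD of the within-subject change. If it is not, give the assumed before-after correlation and recalculate.
2. Replace the 85% claim with what the planned number provides, for example: *With an SD of change of 0.4 g/day, 12 completers give 79% power for a difference of 0.3 g/day (one-sided 5% paired t-test); 85% power is reached at 0.33 g/day.* For 11 completers the figures are 75% and 0.35 g/day.
3. Name one primary test in section 8.5.1 and quote the power for that test. For the exact one-sided Wilcoxon with normally distributed changes it is about 75% at 12 completers and 70% at 11.
4. Keep one rule for the number 12 in sections 1.2, 3.4, 3.9.1, 3.10.2 and 8.2: either 12 enrolled without replacement (10 to 11 expected completers), or 12 completers with replacement and no dropout allowance. Delete the other.

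The cost is rewording in these sections and a less favourable stated power. No additional patients are needed.

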8.3 Definitions of analysis sets

Before and after dapagliflozin treatment

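### The sample size for this before-after trial rests on an SD of 0.4 that is not shown to be the SD of within-patient change, and the stated 85% power depends on a before-after correlation the plan never gives.

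*Combined protocol and SAP*

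**What the plan says.** Section 8.2 and the sample size paragraph of section 1.2 carry the same derivation. They cite LDL-apoB poolsize/synthesis in 8 patients before and on rosuvastatin, "2.8 ± 0.4 to 1.5 ± 0.4 gram/day, see ref 22", and expect a "concomitant less decrease in LDL- ApoB poolsize /synthesis (1.8 ± 0.4 gram/day" once dapagliflozin is added. The planned effect is therefore 1.8 − 1.5 = 0.3 g/day. The test is specified as "Using single sided test (with alfa of 0.05 and 85% power", the inputs as "using difference in LDL-apoB synthesis of 0.3 gram/day with SD of 0.4", and the result is that "the sample size needs to be 11 DM2 subjects, on dapagliflozin 10mg treatment". The paragraph ends: "Taking a 10% patient dropout rate, we aim to include 12 DM2 subjects in total".

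The design is single arm. The primary outcome in section 2 is the change in LDL synthesis. Fluxes are measured after 4 weeks of rosuvastatin and again after 5 weeks of added dapagliflozin. Section 8.3 describes the comparison as "Before and after dapagliflozin treatment". Section 8.5.1 lists multivariate analysis, repeated-measures ANOVA and Wilcoxon's signed-rank test without naming one as primary; the signed-rank test is a paired test. Section 3.4 adds a replacement rule, "Patients will be replaced by new patients until all 12 DM2 patients have completed the trial", repeated in 3.9.1 and 3.10.2.

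**The concern.** The power of a paired comparison depends on the SD of the individual changes, not on how widely patients differ at one visit. The two are linked by the before-after correlation, which the plan does not mention. The only LDL-apoB spreads it reports belong to single time points, and each is 0.4, the same number that enters the calculation. No source is given for 0.4 as an SD of change.

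If 0.4 is a single-time spread carried into a paired formula, the stated 85% has no basis in the plan's own inputs. What is at stake is how a null result would be read. At low correlation the trial would have little better than even odds of detecting its planned effect, while at high correlation it would be better powered than stated. The reader cannot tell which applies.

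**Working it through.** **Inputs from section 8.2.** Difference d = 0.3 g/day; SD = 0.4 g/day; one-sided alpha 0.05; power 85%; stated n = 11; target 12. Normal quantiles: 1.645 (alpha), 1.036 (85%), 0.842 (80%).

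**Step 1: the plan's own figure, taking 0.4 as the SD of change.** The one-sample or paired normal formula is n = [SD × (z_alpha + z_power) / d]².

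- 85% power: [0.4 × (1.645 + 1.036) / 0.3]² = 12.78, so 13.
- 80% power: [0.4 × (1.645 + 0.842) / 0.3]² = 10.99, so 11.
- Paired t (noncentral t), 85% power: 15.
- Two independent groups, 85% power: 26 per arm.

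Only a one-sample or paired formula with 0.4 as the SD comes near 11, and 11 is its answer for 80% power, not 85%.

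**Step 2: power with 0.4 as the SD of change.** Normal approximation: power = Φ(d√n / SD − 1.645). Paired t: noncentral t with noncentrality d√n / SD and n − 1 degrees of freedom.

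- n = 11: 0.75 × √11 = 2.487; normal Φ(0.842) = 80%; paired t 75%.
- n = 12: 0.75 × √12 = 2.598; normal Φ(0.953) = 83%; paired t 78% (78.5% before rounding).

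**Step 3: from single-time spread to SD of change.** Assume the spread is 0.4 at both visits; this is an assumption, since 1.8 ± 0.4 is an expectation and not data. Then SD of change = 0.4 × √(2(1 − r)). It equals 0.4 only when 2(1 − r) = 1, that is r = 0.5.

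**Step 4: range over r.** The documents give no r, so these values are assumed. All rows use one-sided 0.05 and a difference of 0.3.

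| r | SD of change | Power n = 11, paired t | Power n = 12, paired t | Power n = 12, normal | n for 85%, paired t |
|---|---|---|---|---|---|
| 0 | 0.566 | 50% | 53% | 58% | 27 |
| 0.3 | 0.473 | 62% | 66% | 71% | 20 |
| 0.5 | 0.400 | 75% | 78% | 83% | 15 |
| 0.6 | 0.358 | 83% | 86% | 90% | 12 |
| 0.7 | 0.310 | 91% | 93% | 96% | 10 |
| 0.8 | 0.253 | 98% | 99% | 99% | 7 |

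The signed-rank test was simulated on normally distributed changes with its exact critical value. At n = 12 it is about 3 points below the paired t for r up to 0.5 (50% at r = 0, 63% at 0.3, about 75% at 0.5), and the gap narrows after that (98% at 0.8).

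**Step 5: the correlation that 85% requires.** Solve power = 85% for the SD of change, then r = 1 − SD² / (2 × 0.4²).

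- 12 completers, paired t: SD at most 0.363, so r at least 1 − 0.1317/0.32 = 0.59.
- 12 completers, normal: SD at most 0.388, so r at least 0.53.
- 11 patients, paired t: SD at most 0.345, so r at least 0.63.
- 11 patients, normal: SD at most 0.371, so r at least 0.57.

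**The case against.** The strongest reply is that the sentence can be read as giving the SD of the difference itself. The plan does not say where 0.4 comes from, and the ± values are not labelled SD or SE. That the figure was carried over from the single-time spreads is an inference from the match, and 0.4 would be correct at r = 0.5. This stands: a reader might conclude that the plan used the wrong SD, but the documents support only that the SD is unsourced and unexplained. The reading does not rescue the stated power, because step 2 takes 0.4 as the SD of change and still falls short of 85%.

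A second reply is that the calculation is a test against the published rosuvastatin value of 1.5, treated as fixed. Section 1.2 does say that the effect of rosuvastatin alone is already established and uses this to justify a single arm. A single-time SD would suit such a test. But the plan measures its own baseline, defines the outcome as a change and lists a paired test; and the one-sample formula is the one in step 1, so 11 patients would still not give 85%.

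A reader might also infer that the trial is underpowered. The documents do not support that either. The low figures need a low r, for which there is no evidence, and with 12 completers an r of 0.6 or more exceeds 85% on the paired t. Because the plan replaces dropouts until 12 complete, 12 is the relevant number, and the 11-patient threshold of 0.63 overstates what is required.

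Finally, this is a pilot. It nevertheless states a formal one-sided test, a power and a derived sample size, and these should follow from their inputs.

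**Conclusion.** The point holds as a gap in the justification. The plan does not show that 0.4 is the SD of within-patient change, and it gives no correlation from which that SD could be derived. Two separate things lie behind the 85%. One is arithmetic: with 0.4 taken at face value, power is 75% to 80% with 11 patients and 78% to 83% with 12 completers (paired t to normal approximation). The other is the unstated correlation: over r from 0 to 0.8, paired-t power with 12 completers spans 53% to 99%, and 85% requires r of about 0.59 or more, equivalently an SD of change of at most about 0.36 g/day. Correcting the arithmetic alone would leave the second question open.

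These results assume normally distributed changes, equal spread of 0.4 at both visits, the plan's own 0.3 g/day effect and its one-sided 0.05 level. The r values are illustrative. True power may be above or below 85%.

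**What to change.** In sections 8.2 and 1.2:

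- Say whether 0.4 is a single-time SD or an SD of within-patient change, and give its source.
- State the assumed before-after correlation and the reason for it.
- Replace the single 85% figure with power at 12 completers for the paired test that will be used, over a plausible range of r.

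The cited rosuvastatin study reports values before and on treatment in 8 patients, so a paired SD may be obtainable from it. It should be used only as a labelled rough guide: it reflects the response to starting a statin (20 mg rosuvastatin, by the study's title), not to adding dapagliflozin to a stable statin.

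The cost is a few sentences. Enrolment and the analysis need not change. The downside is a power statement that is less definite and may look less favourable.

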8.3 Definitions of analysis sets

Before and after dapagliflozin treatment

8.3.1 Efficacy analysis set

Effect dapagliflozin on HDL catabolic fractional rate and plasma CETP levels

Effect dapagliflozin on triglyceride/VLDL synthesis rate and liver fat MRI signal

Effect dapagliflozin on hepatic and peripheral insulin sensitivity

8.3.2 Safety analysis set

n/a

8.3.3 PK analysis set

n/a

8.3.4 PRO analysis set

n/a

8.4 Outcome measures for analyses

8.5 Methods for statistical analyses

8.5.1 Analysis of the primary variable(s)

All data will be analysed using SPSS for Windows, version 20.0 (SPSS Inc. Chicago, Illinois, USA). Multivariate analysis and ANOVA for repeated measures will be used. Wilcoxon's signed-rank test will be used to compare results between the study groups. Data will be expressed as median and range. Spearman's rank test will be used to calculate correlations.

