Clinical Study Protocol

Drug Substance Dapagliflozin

Study Code DICE study

Edition Number Version 5

Date 27-06-2015

Dapagliflozin on cholesterol metabolism in DM2: dissecting its effect on dyslipidemia by using stable isotope based cholesterol and glucose fluxes; a pilot study

Sponsor:

The following Amendment(s) and Administrative Changes have been made to this protocol since the date of preparation:

Amendment No.	Date of Amendment	Local Amendment No:	Date of Local Amendment
_____	_____	_____	_____
_____	_____	_____	_____

Administrative Change No.	Date of Administrative Change	Local Administrative Change No.	Date of Local Administrative Change
_____	_____	_____	_____
_____	_____	_____	_____
_____	_____	_____	_____

PROTOCOL SYNOPSIS

Dapagliflozin on cholesterol metabolism in DM2: dissecting its effect on dyslipidemia (DICE study)

Principal Investigator

Prof dr [name], internist-endocrinologist AMC-VUMC, Amsterdam, the Netherlands

Study site(s) and number of subjects planned

AMC-VUMC Diabetes Center, 12 DM2 subjects to be included

Study period	Phase of development	
Estimated date of first subject enrolled	Q4 2015	Phase III/IV
Estimated date of last subject enrolled	Q4 2017	Phase III/IV
Dataanalyses and modelling	Q1 2018	

Study design

Single arm intervention trial

Objectives

Primary Objective:	Outcome Measure:
effect of 5 weeks dapagliflozin 10mg on LDL cholesterol in patients with DM2	Change in LDL synthesis

Secondary Objective:	Outcome Measure :

Effect of 5 weeks dapagliflozin 10mg on and Triglyceride cholesterol fluxes
 
Effect of 5 weeks dapagliflozin 10mg on insulin sensitivity and energy expenditure
 
Effect of 5 weeks dapagliflozin 10mg on liver fat content (MRI liver)
	
Change in VLDL secretion and clearance (as determined by $^2\text{H}_3$ Leucine enrichment) and relation to plasma CETP, PLTP and HDL subfractions
 
Change in De novo lipogenesis (as determined by $^2\text{H}_2\text{O}$ deuterated 'heavy' water)
 
oral $1,2,3,4-^{13}\text{C}_{16}$ – palmitate to measure FFA remnant uptake.
 
Change in hepatic and peripheral insulin sensitivity (2 step Hyperinsulinemic normoglycemic clamp with $^2\text{H}_2$ enriched glucose:) and energy expenditure including carbohydrate oxidation and fatty acid oxidation rates in breathing air
 
Change in liverfat MRI spectrum

---	--

Target subject population

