Male or postmenopausal female patients with type 2 diabetes BMI > 25 kg/m² and more than 12 weeks a stable dose of metformin treatment > 1500mg (HbA1C \geq 6.5% - <8.5%) FPG<132 mmol/l, LDL cholesterol >2.5 mmol/l, willing to switch to rosuvastatin 10mg once daily for 4 weeks, and then receive 10 mg dapagliflozin once daily orally, for 5 weeks. Measurements (lipid and glucose fluxes) will be done after 4 weeks of rosuvastatin treatment (baseline) and after 5 weeks of dapagliflozin

Duration of treatment

4 weeks of crestor 10mg once daily treatment in all subjects (baseline) and after 5 weeks of dapagliflozin (n=12 DM2 subjects)

Investigational product, dosage and mode of administration

Crestor 10 mg once daily for in total 9 weeks orally

Dapagliflozin 10mg once daily for 5 weeks orally

Statistical methods

All data will be analysed using SPSS for Windows, version 20.0 (SPSS Inc. Chicago, Illinois, USA). Multivariate analysis and ANOVA for repeated measures will be used. Wilcoxon's signed-rank test will be used to compare results between the study groups. -Data will be expressed as median and range.

	PAGE
TABLE OF CONTENTS	
TITLE PAGE	1
PROTOCOL SYNOPSIS.....	2
TABLE OF CONTENTS.....	5
LIST OF ABBREVIATIONS AND DEFINITION OF TERMS	9
1. INTRODUCTION	10
1.1 Background and rationale for conducting this study	10
1.2 Rationale for study design, doses and control groups.....	10
1.3 Study Design.....	12
2. STUDY OBJECTIVES.....	16
2.1 Primary objective	16
2.2 Secondary objectives	Fout! Bladwijzer niet gedefinieerd.
2.3 Safety objectives	16
2.4 Exploratory objectives	17
3. SUBJECT SELECTION, ENROLMENT, RANDOMISATION, RESTRICTIONS, DISCONTINUATION AND WITHDRAWAL.....	17
3.1 Inclusion criteria	17
3.2 Exclusion criteria	17
3.3 Subject enrolment and randomization	17
3.4 Procedures for handling incorrectly enrolled or randomized subjects.....	17
3.5 Methods for assigning treatment groups.....	18
3.6 Methods for ensuring blinding.....	18
3.7 Methods for unblinding.....	18
3.8 Restrictions	18
3.9 Discontinuation of investigational product.....	18
3.9.1 Procedures for discontinuation of a subject from investigational product	18
3.10 Criteria for withdrawal.....	18
3.10.1 Screen failures.....	18
3.10.2 Withdrawal of the informed consent.....	18
3.11 Discontinuation of the study	18

4.	STUDY PLAN AND TIMING OF PROCEDURES.....	18
4.1	Enrolment/screening period	21
4.2	Treatment period.....	21
4.3	Follow-up period.....	21
5.	STUDY ASSESSMENTS	21

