1.2 Rationale for study design, doses and control groups

Study Hypothesis and rationale

Dapagliflozin 10mg once daily for 5 weeks increases hepatic LDL and VLDL secretion driven by altered CETP in DM2 patients on stable statin therapy (10mg rosuvastatin once daily)

Study design:

Male or postmenopausal female patients with type 2 diabetes (BMI > 25 kg/m² and more than 12 weeks a stable daily dose of metformin treatment > 1500mg) with good glycemic control (HbA1C \geq 6.5% - < 8.5% and fasting plasma glucose < 132 mmol/l) and on stable statin regimen and willing to switch to crestor 5 mg once daily during the study. After 4 weeks of rosuvastatin treatment (20), baseline measurements for glucose and lipid fluxes will be performed and thereafter DM2 patients will be randomized to receive 10 mg dapagliflozin (n=12) orally with rosuvastatin 10mg once daily. Measurements (lipid and glucosefluxes) will be repeated after 5 weeks of dapagliflozin treatment.

Sample size

Previous studies have reported a 10 % increase in fasting plasma LDL plasma levels upon dapagliflozin 10mg once daily treatment in DM2 patients on statin therapy (20). As it can be expected that metabolic effects of SGLT2 inhibition stabilize after 4 weeks (5,6) and lipid fluxes upon intervention are usually determined upon 4-5 weeks after start of intervention (21), we suggest to treat for 5 weeks. A reduction was seen in 8 DM2 subjects of plasma LDL (from 3.1 ± 0.8 to 1.5 ± 0.4 mmol/l) on rosuvastatin treatment, that corresponded with a similar decrease in LDL- ApoB poolsize /synthesis (2.8 ± 0.4 to 1.5 ± 0.4 gram/day, see ref 22). We thus expect 10% higher plasma LDL level (from 3.1 ± 0.8 to 1.7 ± 0.4 mmol/l) with concomitant less decrease in LDL- ApoB poolsize /synthesis (1.8 ± 0.4 gram/day) upon rosuvastatin combined with dapagliflozin 10mg treatment in DM2. Using single sided test (with alfa of 0.05 and 85% power) and using difference in LDL-apoB synthesis of 0.3 gram/day with SD of 0.4, the sample size needs to be 11 DM2 subjects, on dapagliflozin 10mg treatment. Taking a 10% patient dropout rate, we aim to include 12 DM2 subjects in total.

Benefit/risk and ethical assessment

Both rosuvastatin and dapagliflozin have been approved by FDA/EMEA and are widely prescribed. The effect of rosuvastatin alone on lipidfluxes in this group of DM2 patients has already been established (22) which thus allows us to study the mere effect of SGLT2 on

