2. STUDY OBJECTIVES

Primary objective Objectives

Primary Objective:	Outcome Measure:
effect of 5 weeks dapagliflozin 10mg on LDL cholesterol in patients with DM2	Change in LDL synthesis

Secondary Objective:	Outcome Measure :
Effect of 5 weeks dapagliflozin 10mg on and Triglyceride cholesterol fluxes	Change in VLDL secretion and clearance (as determined by ² H ₃ Leucine enrichment) and relation to plasma CETP, PLTP and HDL subfractions Change in De novo lipogenesis (as determined by ² H ₂ O deuterated 'heavy' water) oral 1,2,3,4- ¹³ C ₁₆ – palmitate to measure FFA remnant uptake.
Effect of 5 weeks dapagliflozin 10mg on insulin sensitivity and energy expenditure	Change in hepatic and peripheral insulin sensitivity (2 step Hyperinsulinemic normoglycemic clamp with ² H ₂ enriched glucose:) and energy expenditure including carbohydrate oxidation and fatty acid oxidation rates in breathing air
Effect of 5 weeks dapagliflozin 10mg on liver fat content (MRI liver)	Change in liverfat MRI spectrum

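### Does the plan leave open which test, and which side, decides the primary change in LDL-apoB synthesis?

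*Combined protocol and SAP*

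**What the plan says.** The synopsis describes the trial as a "Single arm intervention trial". On timing it says: "Measurements (lipid and glucose fluxes) will be done after 4 weeks of rosuvastatin treatment (baseline) and after 5 weeks of dapagliflozin". Section 1.2 agrees that the flux measurements "will be repeated after 5 weeks of dapagliflozin treatment", and 8.3 sets the comparison as before against after dapagliflozin.

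The primary outcome in section 2 is "Change in LDL synthesis". Section 8.2 sizes the trial on it: "Using single sided test (with alfa of 0.05 and 85% power) and using difference in LDL-apoB synthesis of 0.3 gram/day with SD of 0.4". That gives 11 patients, rounded up to 12 for dropout, and sections 3.4 and 3.9.1 replace patients until 12 have completed. The hypothesis in 1.2 is that dapagliflozin raises hepatic LDL and VLDL secretion.

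Section 8.5.1, headed as the primary analysis, says "Multivariate analysis and ANOVA for repeated measures will be used. Wilcoxon's signed-rank test will be used to compare results between the study groups". Section 8.5.2 repeats the text for the secondary variables, and the synopsis has the same method sentences. None of the three gives a side or a level, and the only summary mentioned is median and range.

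**The concern.** Three methods are listed for all data and none is marked as decisive. On a two-occasion outcome, repeated-measures ANOVA is a two-sided paired t-test, so one listed method does not match the one-sided basis of 8.2. The phrase "Wilcoxon's signed-rank test will be used to compare results between the study groups" speaks of groups in a trial that has only one.

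With 12 patients the choice could matter. If side and method were both open, power for the planned 0.3 g/day would run from about 61% (two-sided signed-rank) to 78% (one-sided paired t). The one-sided and two-sided signed-rank tests would disagree in about 14% of trials. Declaring a result when either the one-sided signed-rank test or the ANOVA was significant would carry a 7.1% error rate when there is no effect. Median and range would also not show how precisely the change was estimated.

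**Working it through.** **Inputs.** Difference 0.3 g/day, SD 0.4, one-sided alpha 0.05, power 85%, n = 11 (8.2); 12 completers (3.4, 3.9.1). Section 8.2 does not say whether 0.4 is the SD of the within-patient change. I assume that it is. If it is the SD on each occasion, with within-patient correlation r, the SD of change is 0.4·√(2(1 − r)): 0.566 at r = 0, 0.400 at r = 0.5 and 0.283 at r = 0.75.

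**The plan's own figure.** The paired normal formula is n = [SD·(z_alpha + z_power)/difference]².
- One-sided 0.05 and 85% power: [0.4 × (1.645 + 1.036)/0.3]² = 12.8, so 13.
- One-sided 0.05 and 80% power: [0.4 × (1.645 + 0.842)/0.3]² = 10.99, so 11.
- Two-sided 0.05 and 85% power: 15.96, so 16.

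The stated 11 equals the one-sided 80% result and is two below the one-sided 85% result. It is much further from the two-sided 16, so the one-sided statement was the basis of the calculation. The shortfall from 85% power is a separate sample-size question that the wording of 8.5.1 does not affect.

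**Power at n = 12, difference 0.3.** The t-test and ANOVA use the noncentral t. The signed-rank test is simulated with exact critical values: W ≥ 61, one-sided level 0.0461; W ≥ 65, two-sided level 0.0425.

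| SD of change | One-sided signed-rank | One-sided paired t | Repeated-measures ANOVA | Two-sided signed-rank |
|---|---|---|---|---|
| 0.283 | 95.2% | 96.3% | 91.6% | 88.8% |
| 0.400 | 75.6% | 78.5% | 65.8% | 61.1% |
| 0.566 | 50.1% | 53.1% | 38.9% | 34.9% |

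**Splitting the spread at SD 0.4.**
- Method alone, both tests one-sided: 78.5 − 75.6 = 2.9 points.
- Side alone, signed-rank: 75.6 − 61.1 = 14.5 points.
- Side alone, paired t: 78.5 − 65.8 = 12.7 points.

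Side dominates, and side is what 1.2 and 8.2 state. With it fixed, the signed-rank test and paired t reach different verdicts in about 5% of trials under the planned effect.

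**False positives with no effect, n = 12.**
- One-sided signed-rank alone: 4.61%.
- Signed-rank or an upward ANOVA result: 4.64%.
- Signed-rank or any ANOVA result: 7.1%. About 2.5 points of this come from ANOVA showing a significant decrease (4.6 + 2.5 = 7.1), which could not support a hypothesis of increase.
- Free choice between one-sided signed-rank (4.6%) and one-sided paired t (5.0%), which disagree in 1.5% of null trials: (4.6 + 5.0 + 1.5)/2 ≈ 5.6%.

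**Precision.** The 95% half-width is 2.201 × SD/√12: 0.254 g/day at SD 0.4, 0.180 at 0.283 and 0.359 at 0.566. Any of these can be calculated from the 12 paired values the plan already collects.

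**The case for a change.** The strongest case for a change is that 8.5.1 is the section headed as the primary analysis, yet it names neither the variable, nor the deciding test, nor the side. Section 8.2 gives a side but no test. ANOVA stands beside the signed-rank test with no order between them, and its F test has no direction. The efficacy lists in 5.1 and 8.3.1 do not include LDL-apoB synthesis, so they do not help. A pilot that powers a hypothesis test still needs one stated test, and a small trial needs an interval more than a large one does. The clarification would cost a few sentences.

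The textual part of this stands: the deciding test is never named in so many words, and the reference to study groups is loose. What does not stand is the inference that the verdict is open. The signed-rank test is a paired test, it alone is given a comparison, and in a single-arm trial the only pair is before and after. ANOVA and multivariate methods have natural uses elsewhere, for the serial samples and the two-step clamp in 1.3. The large figures (61% to 78% power, 14% disagreement, 7.1% error) depend on ignoring the stated side or on counting a significant decrease as success. Planning to show median and range does not prevent reporting an interval.

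**Conclusion.** The concern does not call for a change. Read together, 1.2, 8.2, 8.3 and 8.5.1 give a one-sided signed-rank test at 0.05 on the within-patient change, after minus before dapagliflozin, and that is a sound primary analysis. What is missing is detail that a competent analyst would supply in this way, together with a clerical slip over groups.

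The choice that truly remains, signed-rank or paired t on the stated side, is worth about 3 points of power and about 5% of verdicts under the planned effect. Even a free choice between the two gives an error rate of about 5.6%. These two results assume 12 completers, normally distributed changes and an SD of change of 0.4; the power gap is 1 to 3 points across SDs of 0.283 to 0.566. An interval with a half-width of about 0.25 g/day (0.18 to 0.36 over that range) would help the reader, but its absence from the text does not make the planned test wrong.
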